## Study Protocol

### **2.A.3. Research Design and Methods.**

**2.A.3.a. Approach.** To test the feasibility of a group-based education and skill-building rehabilitation (ESBR) intervention in improving dementia caregiver and care recipient outcomes, our proposed trial will consist of 40 family caregivers coping with all-cause dementia who will be randomized to ESBR. Twenty participants will be randomized to receive mobile media ESBR (ESBR-m), and 20 participants will be randomized to receive usual care plus supplemental educational materials on dementia (UC).

The results of this project will determine the efficacy of a low-cost, pragmatic intervention for caregivers of Veterans with all-cause dementia and will be used to build upon prior findings indicating the efficacy of resource-intensive methods to rehabilitate caregivers of Veterans with all-cause dementia.

#### **2.A.3.b. Participants**

Inclusion criteria - Participants must:	Exclusion criteria - Participants will be excluded for:

• be adults (age <math>\geq 18</math>)

• report distress associated with being the primary caregiver for a family member with dementia

• reporting at least 2 of the following 6 items at baseline assessment: felt overwhelmed, felt like they often needed to cry, were angry or frustrated, felt they were cut off from family or friends, reported moderate to high levels of general stress, or felt their health had declined

• provide at least 7 hours of care (supervision or direct assistance) per week over the past 3 months (other sources of caregiving for the Veteran with dementia can also be utilized; e.g., respite, home health aide, other family members)

• cohabitate with a Veteran diagnosed with dementia

• be proficient in spoken and written English

• be capable of providing informed consent

	

• current or lifetime history of any psychiatric disorder with psychotic features

• prominent suicidal or homicidal ideation

• having met DSM-IV criteria for drug or alcohol abuse or dependence (except nicotine) within the past six months

• presence of alcohol intoxication (by breathalyzer) or alcohol withdrawal (by exam) during study recruitment or participation

• diagnosis of probable or possible dementia

• a Telephone Cognitive Screen score of <math>< 20</math>

• participation in another caregiver intervention study within the past year

• lack of access to telephone and internet services in the home

• illness that would prevent study participation

• planned transfer of care receiver to another caregiver or nursing home within 6 months

**2.A.3.c. Recruitment.** We aim to recruit 40 participants who meet inclusion/exclusion criteria for the proposed project (ESBR-m:  $n = 20$ ; UC:  $n = 20$ ). Participants will be recruited primarily from the VA Palo Alto Health Care System (VAPAHCS). We anticipate primary referral sources to include: Sierra-Pacific Mental Illness Research Education and Clinical Center (directed by [name]); VAPAHCS Dementia Committee (chaired by [name], PI); VA Memory Clinic (directed by [name]); Geriatric Research, Education, and Clinical Center; Stanford/VA Aging Clinical Research Center (directed by Drs. [name] and [name]); Stanford/VA Alzheimer's Research Center (co-directed by [name]); Psychology and Psychiatry Services ([name] is ACOS for Mental Health); and the War Related Illness and Injury Study Center ([name], see support letter, serves as Director of Research). Based on clinical experience in the VA Memory Clinic, we also expect primary care clinics to serve as key referral resources. [name], Associate Chief of Staff for Ambulatory Care at VAPAHCS, has designated resources to our team to aid with recruitment in Patient Aligned Care Team (PACT; i.e., primary care) clinics. Additional participants will be recruited from the Veteran community via word of mouth, an IRB-approved recruitment flyer, and public and private speaking engagements. These additional recruitment avenues have been highly successful in providing subject pools for prior studies from our group. Given our Center's experience in participant recruitment, participants' response to a pilot of the intervention, and high prevalence (80%) of home broadband internet access in the San Francisco Bay Area (Baldassare, Bonner, Petek, & Shrestha, 2013), we expect ample ability to meet our enrollment goals. In the interest of maintaining recruitment of an adequate number of participants, we will supplement our Veteran sample with non-Veterans, if necessary.

**2.A.3.d. Retention.** We will implement several procedures to enhance recruitment and study retention. First, we will provide remuneration (\$25) for each study event. We will also provide telephone and electronic/mail reminders of upcoming appointments. We will also be flexible in scheduling appointments to accommodate the participant's schedule. Furthermore, we will make a strong effort to "personalize" each participant's

experience. For example, we will send out thank you cards to all participants and will make follow-up telephone calls to express gratitude for participation. We will follow procedures that we have successfully used in our previous research.

**2.A.3.e. Screening Procedures.** Participant screening for eligibility and other data collection will mainly occur during telephone interviews. Should caregivers prefer, face-to-face (in-person) screening/assessment will also be offered. An interview will be conducted with caregivers to determine study eligibility. During this interview, study staff will explain the study, its requirements, and answer any questions the potential participant may have. Upon the potential participant's willingness to be screened, study staff will ensure all inclusion criteria are met and screen the potential participant for all exclusionary criteria. The results of all screening assessments will be reviewed by the PI in consultation with Co-I's. After consensus determination of study eligibility, the Study Coordinator will contact the participant to schedule a Baseline assessment (if eligible), or provide appropriate referral (e.g., VA Caregiver Support Program) and explanation (if not deemed eligible). Both "screen failures" and eligible participants who drop out prior to receiving any intervention will be replaced.

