### **2.A.3.f. Procedures Involving Eligible Participants**

#### **2.A.3.f.1. Enrollment, Randomization, and Baseline Assessment**

Enrollment and Randomization. Once participants are deemed eligible, they will be invited by the Study Coordinator to participate in the study, if willing and able to provide informed consent. At this point, the Data Manager will randomize the participant to one of two arms: ESBR-m or UC. For randomization, a modification of the Efron procedure (Efron, 1971) developed by [name] (Kraemer, 1981) will be implemented to assure the two groups are comparable at baseline in terms of dementia subtype. Participants who drop out after receiving any intervention will not be replaced, but their data will be used in mixed-effects analyses.

Baseline Assessment. Trained study staff, blind to the participants' ESBR-m/UC assignment, will administer a baseline assessment including clinicodemographics and measures of caregiver burden, depression, and perceived stress, in addition to care recipient functional status (see Section 2.A.3.g. for a description of outcome measures). Assessment will mainly occur over the telephone to reduce study participation burden. Packets with assessment aids will be sent to the caregiver prior to each assessment. Should caregivers prefer, in-person assessments will also be offered.

Mental Health referrals to Stanford Outpatient Psychiatry Clinics will be offered to all participants who score 16+ on the CES-D, in addition to participants who endorse symptoms of significant clinical concern, as determined by study staff. All participants are also provided information on accessing the VA Caregiver Support Program and the Veterans Crisis Line.

**2.A.3.f.2. Mobile Media Education and Skill-Building Rehabilitation Intervention (ESBR-m).** Our ESBR-m intervention consists of four, 90-minute group ( $\leq 5$  participants) sessions. **These four sessions are supplemented with a booster session one month following the last intervention session.**

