While prior studies have reported barriers to engaging dementia caregivers in treatments delivered via the internet, these issues were related to challenges with more complicated tasks performed with personal computers (Hayden, Glynn, Hahn, Randall, & Randolph, 2012) (e.g., entering a chat room, downloading streaming videos). Our novel intervention and our use of customized tablets alleviates many of the technical hurdles faced by previously developed internet interventions. Tablets offer several advantages over traditional computer-delivered interventions including 1) a pared down, user friendly interface; 2) increased access due to relative affordability in comparison to traditional computers; 3) integrated availability of video telehealth service provision; 4) ultimate portability; and 5) ease of delivering prepackaged content and services. Content (e.g., skill-building videos, multimedia relaxation facilitation, challenging behavior tipsheets) will be prepackaged on the tablets and will be available offline, making the tablets a fully portable resource for caregivers.

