#### **2.A.3.f.3d. ESBR-m Session 4 – Dementia: How can I cope with the stress caused by dementia?**

Session 4 objectives are to:

- build caregiver coping skills (~45 minutes)
- solidify the importance of self-care (review) (~15 minutes)
- review of learned relaxation techniques (~30 minutes)

Session 4 is designed to improve the caregiver's coping skills, specifically targeted to address the challenges of being a dementia caregiver. Ways to manage common symptoms of dementia syndromes using concrete examples, provided both by the leader of the session and caregiver participants, are demonstrated and practiced in role play. The intervention leader will aid participants in reframing cognitive, behavioral, and psychiatric symptoms of dementia as manifestations of damage to the brain.

Targeted skill-building to address care recipient symptoms elicited from participants is integrated into the session to maximize training in skills pertinent to the group. Non-pharmacological interventions for dementia symptom management from previous sessions are reviewed and consolidated.

Self-care activities from the previous sessions are discussed; importance of continued self-care is solidified.

The relaxation techniques covered in Sessions 1-3 are reviewed and consolidated. Continued use post-intervention is encouraged with participants setting ongoing goals for implementation.

**2.A.3.f.3e. ESBR-m Booster Session.** The 90-minute booster session (1-month after the final intervention session) is designed to briefly review dementia knowledge and resources available to dementia patients and their caregivers. Caregiving skills, as they pertain to current stressors, are honed in a manner that is tailored to the small group's needs. The importance of continued self-care is accentuated. Intervention relaxation techniques are revisited and continued use is fostered.

**2.A.3.f.4. Usual Care (plus supplemental educational materials).** Participants randomized to the Usual Care (UC) group will receive supplemental educational materials (e.g., VA Caregiver Support Program; Veterans Crisis Line; National Institute on Aging's "Understanding Memory Loss").

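### The replacement rule turns on receipt of intervention rather than on randomisation, so it reaches caregivers already randomised and, on its natural reading, conflicts with intention to treat

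*Protocol*

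**What the plan says.** Protocol 2.A.3.e (Screening Procedures) provides that, besides screen failures, "eligible participants who drop out prior to receiving any intervention will be replaced".

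Protocol 2.A.3.f.1 places allocation at enrolment, once eligibility and consent are settled: "At this point, the Data Manager will randomize the participant to one of two arms". It then describes study staff who, "blind to the participants' ESBR-m/UC assignment, will administer a baseline assessment". The sessions come later, in 2.A.3.f.2 onward. The randomisation paragraph also holds the companion rule: "Participants who drop out after receiving any intervention will not be replaced, but their data will be used in mixed-effects analyses".

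Protocol 2.A.3.a states the size as numbers randomised: "Twenty participants will be randomized to receive mobile media ESBR (ESBR-m), and 20 participants will be randomized to receive usual care" with educational materials. Section 2.A.3.c gives 40 as the recruitment aim.

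SAP 2.A.3.i describes the project as a feasibility study, plans mixed-effects models on baseline and follow-up data, and names intention to treat as the principle for missing outcomes. It defines no analysis set and does not mention replaced participants.

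**The concern.** The boundary that matters for a randomised comparison is randomisation. The replacement rule uses a later one. Between the two lies a period in which a caregiver has an allocation but has had no session, and anyone who leaves in that period is to be replaced.

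Two things are at stake. First, if replaced people are also dropped from the count, losses between allocation and first session vanish from the denominator, in a project whose stated purpose is feasibility. Second, if they are dropped from the analysis, the groups compared are starters, not the groups that were randomised.

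The arms may also lose people unequally in that period. ESBR-m is given in groups of up to five, so a participant may have to wait for a group. For usual care the text says only that "Participants randomized to the Usual Care (UC) group will receive supplemental educational materials", and follow-up in that arm is timed from assignment. The documents give neither a waiting time nor a loss rate.

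**Working it through.** **Reading the passages together**

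1. Order of events in 2.A.3.f.1: eligible and consented, then randomised, then baseline by staff blind to an existing assignment, then sessions. Even if baseline in practice came before allocation, allocation would still precede the sessions, which is all this point needs.
2. The rule in 2.A.3.e applies up to the first intervention. It therefore covers people randomised but not started.
3. The companion rule in 2.A.3.f.1 splits drop-outs at the same place and promises use of data to the later group only. Nothing is said about data from the earlier group.
4. The plan is 20 + 20 = 40 randomised, which agrees with 2.A.3.c. Replacement after randomisation takes the number randomised above 40 unless replaced people are not counted.

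**Feasibility count** (p = assumed non-start after allocation, 10–20%; the documents give none)

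- True start rate = 1 − p: 90% at p = 0.10 and 80% at p = 0.20. With replaced people uncounted it appears as 100%.
- Randomised per arm for 20 expected starters = 20/(1 − p): 22.2, rounded up to 23, at p = 0.10; 25 at p = 0.20. At 1:1 the total is 46 to 50, against the planned 40.

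**Outcome comparison if replaced people are excluded** (assumed: loss 10–20 points higher in ESBR-m; leavers differ by 0.5 SD; baseline–follow-up correlation r = 0.6, range 0.4–0.8)

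- Standard error with 20 per arm = √(2/20) = 0.316 SD. Baseline-adjusted at r = 0.6: 0.316 × √(1 − 0.36) = 0.253 SD.
- Bias = differential loss × gap that remains after any adjustment.
- Same gap at baseline and follow-up, change comparison: 0.
- Same persistent gap, baseline-adjusted: 0.5 × (1 − 0.6) = 0.20, so 0.10 × 0.20 = 0.02 to 0.20 × 0.20 = 0.04 SD, or 0.08–0.16 of the standard error. Over r = 0.4–0.8 the range is 0.10 × 0.10 = 0.01 to 0.20 × 0.30 = 0.06 SD.
- Gap fully predicted by baseline, baseline-adjusted: 0.
- Gap arising wholly after baseline: 0.10 × 0.5 = 0.05 to 0.20 × 0.5 = 0.10 SD, or 0.20–0.40 of the standard error. With the gap varied over 0.3–0.8 SD, this case runs from 0.10 × 0.3 = 0.03 to 0.20 × 0.8 = 0.16 SD.

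**What keeping leavers can recover** (loss in ESBR-m only)

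- If a fraction f of leavers give follow-up and are typical of leavers, the share of bias removed = 1 − (1 − p)(1 − f)/(1 − p + pf). At f = 0.5: 1 − 0.45/0.95 = 0.53 (p = 0.10) and 1 − 0.40/0.90 = 0.56 (p = 0.20). At f = 0 it is 0.
- Keeping leavers who have baseline data only is not always an improvement. In a mixed model with separate baseline means by arm and a persistent gap, it shifts the change contrast by p × gap × (1 − r) = 0.10 × 0.5 × 0.4 = 0.02 to 0.20 × 0.5 × 0.4 = 0.04 SD, where exclusion gave 0.

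**The case against.** The best defence is that no sentence excludes replaced people. The replacement rule stands under Screening and may have been written with the not-yet-randomised in mind. The only governing analysis text favours using all outcome data under intention to treat. The companion rule is silent on earlier leavers, and silence is not exclusion. The 20 + 20 is weak evidence too: 2.A.3.c treats 40 as an aim, and a modified Efron allocation does not force an exact split.

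Much of this stands. Exclusion is implied, not stated, and a reader who infers that the plan openly prescribes a starters-only analysis goes beyond the text. But the rule's wording is not confined to screening, the randomisation paragraph adopts the same cut-off, and one general reference to intention to treat does not say what happens to someone who has been replaced.

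Two further inferences are tempting and not supported:

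- A reader might infer that screen failures can also be randomised already, because one inclusion criterion requires "reporting at least 2 of the following 6 items at baseline assessment". But 2.A.3.e has all criteria checked and eligibility agreed before baseline is scheduled, and 2.A.3.f.1 randomises only those found eligible. That is a timing inconsistency in one criterion and a separate matter.
- A reader might infer that handing over the tablet counts as starting, since content "will be prepackaged on the tablets and will be available offline". That sentence concerns content and says nothing of when tablets are issued. Section 2.A.3.f.2 describes the intervention as four group sessions, so the first session is the natural start.

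It is also fair that the start rate is not named as an endpoint in the supplied text.

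**Conclusion.** The point holds. The replacement rule is set at the wrong boundary: followed as written it replaces randomised caregivers, and with its companion rule it invites a comparison of starters that intention to treat does not allow.

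The effect on outcomes is of unknown size and direction and probably small. With a 0.5 SD gap it is 0 to 0.10 SD, the upper figure needing a gap that arises wholly after baseline; the most extreme case tried gives 0.16 SD. It is zero with equal loss and equal gaps in the two arms. A reader might infer that the treatment comparison is materially biased; the documents give no loss rate or difference from which to show that.

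The firmer consequence is for feasibility. If replaced people go uncounted, a start rate of 80–90% (assumed) is reported as 100%, and a later trial would be planned without knowing the loss between allocation and first session.

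**What to change.** - **Protocol 2.A.3.e:** limit replacement to screen failures and eligible people who withdraw before randomisation.
- **Protocol 2.A.3.f.1 and SAP 2.A.3.i:** state that all randomised participants are counted and analysed in their assigned arm, and are invited to follow-up whether or not they start.
- **If 20 starters per arm are still wanted:** randomise further recruits in the usual way, in addition to those already randomised and not in their place; about 46 to 50 in total at an assumed 10–20% non-start.
- **Reporting:** give the numbers randomised, started and lost before starting, by arm, and say what counts as having started in each arm.

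The cost is wording and a little precision. If the trial stays at 20 per arm and 2 to 4 of the 20 in ESBR-m give no follow-up, the unadjusted standard error goes from 0.316 to √(1/18 + 1/20) = 0.325 or √(1/16 + 1/20) = 0.335 SD, a rise of about 3–6%. The change restores the randomised groups and the denominator, but it does not remove bias where leavers give no follow-up, so the invitation to follow-up matters as much as the definition of the analysis set.

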### **2.A.3.f. Procedures Involving Eligible Participants**

#### **2.A.3.f.1. Enrollment, Randomization, and Baseline Assessment**

Enrollment and Randomization. Once participants are deemed eligible, they will be invited by the Study Coordinator to participate in the study, if willing and able to provide informed consent. At this point, the Data Manager will randomize the participant to one of two arms: ESBR-m or UC. For randomization, a modification of the Efron procedure (Efron, 1971) developed by [name] (Kraemer, 1981) will be implemented to assure the two groups are comparable at baseline in terms of dementia subtype. Participants who drop out after receiving any intervention will not be replaced, but their data will be used in mixed-effects analyses.

Baseline Assessment. Trained study staff, blind to the participants' ESBR-m/UC assignment, will administer a baseline assessment including clinicodemographics and measures of caregiver burden, depression, and perceived stress, in addition to care recipient functional status (see Section 2.A.3.g. for a description of outcome measures). Assessment will mainly occur over the telephone to reduce study participation burden. Packets with assessment aids will be sent to the caregiver prior to each assessment. Should caregivers prefer, in-person assessments will also be offered.

Mental Health referrals to Stanford Outpatient Psychiatry Clinics will be offered to all participants who score 16+ on the CES-D, in addition to participants who endorse symptoms of significant clinical concern, as determined by study staff. All participants are also provided information on accessing the VA Caregiver Support Program and the Veterans Crisis Line.

**2.A.3.f.2. Mobile Media Education and Skill-Building Rehabilitation Intervention (ESBR-m).** Our ESBR-m intervention consists of four, 90-minute group ( $\leq 5$  participants) sessions. **These four sessions are supplemented with a booster session one month following the last intervention session.**

While prior studies have reported barriers to engaging dementia caregivers in treatments delivered via the internet, these issues were related to challenges with more complicated tasks performed with personal computers (Hayden, Glynn, Hahn, Randall, & Randolph, 2012) (e.g., entering a chat room, downloading streaming videos). Our novel intervention and our use of customized tablets alleviates many of the technical hurdles faced by previously developed internet interventions. Tablets offer several advantages over traditional computer-delivered interventions including 1) a pared down, user friendly interface; 2) increased access due to relative affordability in comparison to traditional computers; 3) integrated availability of video telehealth service provision; 4) ultimate portability; and 5) ease of delivering prepackaged content and services. Content (e.g., skill-building videos, multimedia relaxation facilitation, challenging behavior tipsheets) will be prepackaged on the tablets and will be available offline, making the tablets a fully portable resource for caregivers.

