Title: Mobile Tablet Education to Advance Caregiver Health

NCT #: NCT03417219

March 3, 2014

**2.A.3.g. Study Measures.** *Zarit Burden Interview (ZBI)* [1]. Several versions of the ZBI have been used successfully as outcome measures in interventions for dementia caregivers [2, 3]. *Center for Epidemiological Studies-Depression (CES-D)* [4]. The CES-D is frequently used to assess depression in dementia caregivers and has been shown to be sensitive to changes in caregiver depression post intervention [5]. *Perceived Stress Scale (PSS)* [6]. The PSS has been used successfully to measure perceived stress in dementia caregivers [7]. *Global Deterioration Scale (GDS)* [8]. The GDS is a semi-structured rating of functional status in degenerative dementia. It has been successfully used in prior studies of dementia caregiver intervention with adequate reliability [9]. *Telephone Cognitive Screen (T-CogS)* [10]. The T-CogS is a brief mental status examination designed to be administered over the telephone. Scores on the T-CogS strongly correlate with MMSE scores ( $r = 0.88$ ,  $p < 0.001$ ) [11]. An exclusion cutoff score of  $< 20$  on the T-CogS is chosen to match a MMSE cutoff of  $< 23$  [12]. *Caregiver Interview*. All caregivers will also be administered a structured interview to ascertain information on levels of socialization and pleasurable activity participation.

**2.A.3.h. Data Management.** Integrity of data collection, scoring, and entry/verification will be overseen by the MIRECC Data Analyst/Database Manager and the PI.

**2.A.3.i. Statistical Analyses.** While the proposed project is designed to assess study feasibility, to test the hypotheses outlined in the Specific Aims (Section 2) we will use mixed-effects modeling to fully utilize outcome data measured over time (baseline and follow-up assessments) and to better handle missing outcome information in line with the intention to treat principle. [name] will serve as a statistical consultant, given her expertise in clinical trial and mixed modeling methodologies.

1. Zarit, S., *The hidden victims of Alzheimer's disease: Families under stress*. 1985: NYU Press.

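### Randomisation comes before the self-reported baseline, with no rule on when participants learn their arm, and the distress inclusion criterion has two conflicting scoring times

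*Protocol*

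**What the plan says.** **Order and blinding.** Protocol 2.A.3.f.1 takes a participant who is eligible and willing to consent, and continues: "At this point, the Data Manager will randomize the participant to one of two arms: ESBR-m or UC". The next paragraph has staff who are blind to the "ESBR-m/UC assignment, will administer a baseline assessment including clinicodemographics and measures of caregiver burden, depression, and perceived stress". The follow-up section (2.A.3.f.5) likewise blinds assessors only.

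**Eligibility.** The inclusion criteria in 2.A.3.b require "reporting at least 2 of the following 6 items at baseline assessment". The screening section, 2.A.3.e, says that at the screening interview "study staff will ensure all inclusion criteria are met and screen the potential participant for all exclusionary criteria". Only after eligibility is agreed does it say that "the Study Coordinator will contact the participant to schedule a Baseline assessment (if eligible").

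**Replacement.** 2.A.3.e states that "eligible participants who drop out prior to receiving any intervention will be replaced". Section 2.A.3.f.1 adds that those who leave after receiving any intervention are not replaced and that their data are analysed.

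**Analysis.** SAP 2.A.3.i states: "we will use mixed-effects modeling to fully utilize outcome data measured over time (baseline and follow-up assessments"), and gives as a further aim to "better handle missing outcome information in line with the intention to treat principle".

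**The concern.** Assessor blinding does not protect a caregiver's own answers on burden, depression and stress. If caregivers know their arm when they give the baseline, allocation can move the first outcome time point. If that shift fades by follow-up, the group-by-time effect carries it as bias.

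The direction cannot be predicted. Disappointment in usual care, or relief in ESBR-m, would make the baseline contrast flatter ESBR-m. As it faded, usual care would appear to gain on ESBR-m and a real benefit could be hidden. The opposite reactions would favour ESBR-m.

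Two further problems follow from the same order of events:

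- If the distress criterion is scored at baseline, as 2.A.3.b says, a person already randomised can prove ineligible, and no rule covers that case.
- If people who leave between randomisation and first intervention are replaced, losses that depend on the arm can change the groups being compared.

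The SAP calls the project a feasibility study, but it also plans hypothesis tests, and Protocol 2.A.3.a says the results will settle efficacy. Bias in the contrast therefore matters.

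**Working it through.** **Reading the sections together**

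1. *Does randomisation precede baseline?* The opening words of the randomisation sentence in 2.A.3.f.1 mark a time: after eligibility and consent. Blinding baseline staff to an assignment presupposes that the assignment exists. 2.A.3.e says only that baseline follows eligibility. No section places baseline before randomisation.
2. *Is the arm withheld from participants?* The blinding statements in 2.A.3.f.1 and 2.A.3.f.5 concern staff. No text in either document gives a time of disclosure.
3. *When is the distress criterion scored?* 2.A.3.b says at baseline; 2.A.3.e says all criteria are confirmed before baseline is scheduled. Both cannot be followed literally.
4. *Who can be replaced?* Both replacement rules turn on receipt of intervention, not on randomisation. A randomised person who leaves before any intervention falls under the replacement rule. If that person also leaves before baseline, there are no outcome data to analyse.

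**Illustration of size**

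The documents give 20 per arm and no significance level, SD, correlation or effect size, so there is no plan figure to reproduce. Everything below other than the 20 per arm is assumed: a two-sided 5% test, all 40 analysed, baseline-to-follow-up correlation r = 0.6, allocation knowledge separating the arms at baseline by s = 0.1, 0.2 or 0.3 SD, and a fraction f of that shift persisting at follow-up.

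- Change contrast: bias = s(1 − f); SE = √(2(1 − r)) × √(2/20) = √0.8 × √0.1 = 0.283 SD; 38 df.
- Baseline as covariate: size of bias = |r − f| × s; SE = √(1 − r²) × √(2/20) = √0.64 × √0.1 = 0.253 SD; 37 df.

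Rejection rates come from the noncentral t distribution with noncentrality bias/SE.

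| Shift at follow-up | Contrast | Bias (SD), s = 0.1 / 0.2 / 0.3 | Two-sided error |
|---|---|---|---|
| Gone (f = 0) | Change | 0.1 / 0.2 / 0.3 | 6.4 / 10.6 / 17.9% |
| Gone (f = 0) | Covariate | 0.06 / 0.12 / 0.18 | 5.6 / 7.5 / 10.7% |
| Half remains (f = 0.5) | Change | 0.05 / 0.10 / 0.15 | 5.3 / 6.4 / 8.1% |
| Half remains (f = 0.5) | Covariate | 0.01 / 0.02 / 0.03 | 5.0 / 5.1 / 5.2% |
| All remains (f = 1) | Change | 0 (cancels) | 5.0% |
| All remains (f = 1) | Covariate | 0.04 / 0.08 / 0.12, opposite sign | 5.3 / 6.1 / 7.5% |

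*Sensitivity to r*, at s = 0.2 and f = 0, for r from 0.4 to 0.8: 8.7 to 16.4% (change) and 5.8 to 13.0% (covariate).

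*Direction*, at f = 0 and r = 0.6:

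- Bias favouring ESBR-m, change contrast: false claims for ESBR-m rise from 2.5% to 5.3 / 10.2 / 17.7%.
- Bias against ESBR-m, change contrast: false claims for ESBR-m fall to 1.1 / 0.4 / 0.1%. Power for an assumed true benefit of 0.5 SD, with noncentrality (0.5 − s)/0.283, falls from 40.6% to 28.0 / 17.7 / 10.2%.
- Bias against ESBR-m, covariate: with noncentrality (0.5 − 0.6s)/0.253, power falls from 48.6% to 39.5 / 31.0 / 23.3%.

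The SAP does not say which of the two contrasts its mixed model will estimate.

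**The case against.** The strongest reply is that the bias argument rests on silence. The Data Manager randomises, and has no described contact with participants; an assignment held in a data office has not necessarily been disclosed. Consent pages are not among the text available for review and might contain a disclosure rule. This is fair, and it is why the point is worded as what *may* happen. The procedure in 2.A.3.f.1 should still carry the rule.

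It can also be said that the baseline named in 2.A.3.b loosely means the first contact, since the six distress items are not listed among the baseline measures. That is possible, but the two sections still need one time point.

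On replacement, adding a participant does not by itself delete the one who left, and the SAP states an intention-to-treat aim. That helps those with baseline data. It does not help someone who leaves after randomisation and before baseline, who contributes nothing to the mixed model and is replaced.

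The inputs to the size calculation are indeed all assumed apart from the 20 per arm, and the larger figures require the shift to vanish completely. The range runs from nil to material, in either direction. Finally, the Global Deterioration Scale is a semi-structured rating of the care recipient and is less exposed than the three caregiver scales.

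**Conclusion.** The concern holds. As written, randomisation precedes baseline, only assessors are blinded, and no available text withholds the arm from caregivers until baseline is done. The conflict between 2.A.3.b and 2.A.3.e over the distress criterion is real, and the replacement rule can reach people already randomised.

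Whether the baseline would actually be biased, by how much and in which direction cannot be settled from the documents; it depends on disclosure before baseline and on how far any shift fades. This should be fixed. Confidence is medium, because the bias depends on a disclosure step that the documents do not describe.

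**What to change.** - **Reorder 2.A.3.f.1:** consent, full baseline assessment, confirmation of all eligibility criteria, randomisation, then disclosure of the arm to the participant.
- **Reconcile 2.A.3.b and 2.A.3.e:** name one contact before randomisation at which the six distress items are scored.
- **Amend the replacement rule in 2.A.3.e:** replacement applies to people lost before randomisation, and everyone randomised stays in the intention-to-treat set.

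A lighter alternative keeps the present order and adds a sentence withholding the arm until baseline is complete. That protects baseline self-report, but it does not prevent losses between randomisation and baseline, or the randomised-but-ineligible case unless the scoring time is also corrected.

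The cost is protocol wording: the same staff, calls and assessments in a different order. Randomisation would fall somewhat later; the documents give no intervals from which to say by how much. Without replacement after randomisation, a few of the 20 per arm may lack follow-up data. Follow-up self-report remains open to allocation knowledge under any order; the change protects only the baseline.
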